2.3 Study Population

The population of this study comprises adults with moderate to severe periodontitis who meet the inclusion/exclusion criteria as described in the protocol synopsis in Section 2 of the SAP. Approximately 150 subjects will be enrolled with 50 subjects per treatment group. Subjects may be re-screened if they do not fail inclusion criteria #6 (having moderate to severe periodontal disease according to the AAP definition [at least 6 teeth with \geq 6 mm PD and \geq 3 mm CAL at baseline]).

2.4 Treatment Regimens

Group 1: ST266 dosed daily on Days 1-5, 8-12, 22, and 30 and then monthly for 7 months (Days 60, 90, 120, 150, 180, 210, and 240).

Group 2: ST266 dosed 2x/week (with at least one day between treatments) for the first 3 months and monthly for 5 months thereafter (Days 120, 150, 180, 210, and 240).

Group 3: Placebo dosed at the same frequency as Group 1.

2.5 Treatment Group Assignments or Randomization

Randomization will be stratified by site and smoker status (never smoked or quit smoking more than two years ago versus has smoked within the last two years). Randomization will be blocked such that assignment to treatment groups both within sites and within

smoker status will be approximately even (1:1:1). ST266 will be supplied to the study site and prepared for use by trained clinical staff, who will not be the same as the dental professionals evaluating the subjects.

At the 90-Day analysis, one statistician and one programmer will be unblinded in order to generate the unblinded 90-day analysis. Another team of statisticians and programmers will remain blinded until the 270-day analysis at the end of the study.

2.6 Sample Size Determination

One hundred and fifty (150) subjects will be enrolled. The sample size for the study is based on the sample size required to compare treatment with ST266 versus placebo for the primary efficacy endpoint.

The number of subjects was estimated based on two meta-analysis studies that reviewed 50 and 72 articles respectively (Bonito, 2005).

Using the normal approximation for sample size determination for an independent sample t-test, and assuming a PD reduction of 0.5 mm on average (difference in means) with a standard deviation of 0.7 mm, $\alpha=0.05$ (0.025 per comparison, Bonferroni correction), and 85% power, a sample size of 44 per group will be required. The expected dropout rate is approximately 10% based on previous experiments; hence 50 subjects will be enrolled per group.

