## 7.2. Number of Subjects

One hundred and fifty (150) subjects will be enrolled. The sample size for the study is based on the sample size required to reject the null hypothesis for the primary efficacy endpoint which contains two comparisons. Using the normal approximation for sample size determination for two independent samples, t-tests, and assuming a PD reduction of 0.5 mm on average (difference in means) with a standard deviation of 0.7 mm,  $\alpha=0.05$  (Bonferroni corrected,  $\alpha$  0.025 per comparison), and 85% power, a sample size of 44 per group will be required. The expected dropout rate is 20% based on previous experiments and current enrollment trends hence 50 subjects will be enrolled per group. GEE analyses will be performed and therefore, the actual power will be between 85 and 90%.

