3. GENERAL ANALYSIS AND REPORTING CONVENTIONS

For continuous endpoints, the summary statistics will generally include number of subjects with data (n), mean, standard deviation, median, minimum and maximum. No preliminary rounding will be performed; rounding will only occur after analysis. To round, the digit to right of last significant digit will be considered: if < 5 then round down, if ≥ 5 then round up. Means and medians will be presented with one more decimal place than the precision of the data. Standard deviations will be presented with two more decimal places than the precision of the data. Percentages will be presented with one decimal place. Minimums and maximums will be presented with the same precision as the original data.

For categorical endpoints, the summary statistics will generally include: number of subjects randomized and/or dosed, number of subjects with data, and the percentage of those with data in each category. Frequency distributions will be presented as appropriate.

Analysis of the clinical efficacy data will consist of modeling endpoints, including change from baseline in PD, CAL, BOP, and FMPI, with treatment group, patients, smoking status, and investigational site as main effects and adjusting for baseline values of a given endpoint. Post-baseline treatment comparisons will be modeled through a GEE method (with a linear link and exchangeable covariance matrix), adjusting for the baseline value. Methods of analysis for periodontal flora, inflammatory cytokine levels in GCF and in serum, and RBL will be described in separate statistical analysis plans.

Hypothesis testing, unless otherwise indicated, will be two-sided. When confidence intervals are presented, they will be two-sided with a confidence coefficient of 95%. Actual P-values will be reported to 3 decimal places if greater than 0.001. If less than 0.001, the value ' <0.001 ' will be reported.

The statistical software, SAS[®] version 9.3 or above, will be used for all summaries and statistical analyses.

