8. EFFICACY EVALUATION

8.1 Overview of Efficacy Analysis Issues

8.1.1 Handling of Dropouts or Missing Data

All reasonable efforts will be made to minimize missing data. However, there are two possibilities for data being missing. In one case, the measurement associated with an individual pocket may be missing at an evaluation. In this case, the worst previous value for this variable will be imputed for that tooth/pocket. Furthermore, the data from an entire patient may be missing because they withdrew before completing the study. For this imputation, an approach similar to that for each site will be employed. For visits that would follow a patient's premature discontinuation from the study, the worst observation associated with each individual pocket will be imputed for all subsequent visits for that patient and will thus also be carried forward for the 270-day evaluation. Subjects who drop out of the study will not be replaced.

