8.3 Analysis Methods

The Day 270 analyses will be independent of the Day 90 analyses. All primary and secondary efficacy analyses unless otherwise stated will be performed on the ITT population. Unblinding will be performed for the Primary and secondary analyses at Day 270.

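### The stated 85% power is a completers-only figure: the sizing treats dropouts as lost, but the primary ITT analysis keeps them at worst-value scores

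*SAP*

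**What the plan says.** **Sizing.** SAP 2.6 works from a t-test "assuming a PD reduction of 0.5 mm on average (difference in means) with a standard deviation of 0.7 mm", and continues: "0.025 per comparison, Bonferroni correction), and 85% power, a sample size of 44 per group will be required". Enrolment is then raised for dropout: "The expected dropout rate is approximately 10% based on previous experiments; hence 50 subjects will be enrolled per group". The SAP synopsis repeats this. Protocol 7.2 has the same target ("a sample size of 44 per group will be required") and the same 50 per arm, but expects 20% dropout. It adds that, because GEE will be used, actual power will lie between 85% and 90%. No derivation of that range is given.

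**Analysis.** SAP 4 defines ITT as every randomised subject, and SAP 8.3 states: "All primary and secondary efficacy analyses unless otherwise stated will be performed on the ITT population". For a patient who withdraws, SAP 8.1.1 says that "the worst observation associated with each individual pocket will be imputed for all subsequent visits for that patient", and it extends this to the 270-day evaluation. SAP 8.1.2.1 also gives rescued pockets their worst earlier score.

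None of the sample-size text mentions these imputation rules.

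**The concern.** Enrolling extra patients for dropout restores power only when dropouts contribute nothing to the analysis and the remaining completers carry the test. Here each dropout contributes a Day 270 value that discards improvement.

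This can act in two ways. The difference between arms shrinks, because some patients in each arm no longer show a treatment effect. The SD can also grow, because dropouts sit near zero change while completers sit at whatever reduction follows SRP. The sizing formula contains neither effect.

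What is at stake is how a non-significant result is read. A trial thought to have 85% power, or 85% to 90%, would be taken as firmer evidence against a 0.5 mm effect than its primary test can provide.

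**Working it through.** **Inputs from the documents**
- Difference 0.5 mm, SD 0.7 mm, 0.025 per comparison, 85% power, 44 then 50 per arm (SAP 2.6).
- Two-sided testing (SAP 3: "Hypothesis testing, unless otherwise indicated, will be two-sided").
- Dropout 10% (SAP 2.6) or 20% (Protocol 7.2).

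**Assumptions not in the documents**
- Equal dropout in the arms.
- A subject-level t-test as a stand-in for the planned GEE.
- Where stated below, the mean reduction m in placebo completers.

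**1. The plan's own figure.** Normal approximation: n = 2 × [0.7 × (z for 0.9875 + z for 0.85) / 0.5]² = 42.1, so 43. The noncentral t gives 44 (power 85.5%; 84.6% at 43). The stated 44 is reproduced. The dropout step at 10% is also right: 44/0.90 = 48.9, so 49, and 50 covers it.

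**2. What that figure describes.** At 10% dropout, 50 × 0.90 = 45 completers. With dropouts removed, noncentral t power is 86.4%. This is the calculation behind the stated 85%.

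**3. Dropouts kept, dilution only.** Let a share d of each arm carry no treatment effect, with the SD held at 0.7 mm. The difference is 0.5 × (1 − d), and the noncentrality is the difference divided by 0.7 × √(2/50) = 0.14.
- d = 0.10: 0.45/0.14 = 3.21, power 82.4% (83.5% by normal approximation).
- d = 0.20: 0.40/0.14 = 2.86, power 71.9% (73.1% by normal approximation).

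At 20% dropout, removing dropouts would leave 40 completers and 81.6% power. So part of the 20% shortfall is the separate matter that 44/0.80 = 55, not 50. The remaining drop, from 81.6% to 71.9%, is the present point.

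**4. Dropouts kept, with the second cluster.** Read 0.7 mm as the completers' SD, and set every imputed change to 0 with no spread among dropouts. The variance in an arm is (1 − d) × 0.49 + d(1 − d) × μ², where μ is the completers' mean reduction: m on placebo, m + 0.5 on active.

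Example, d = 0.10 and m = 1.0:
- placebo 0.441 + 0.09 × 1.0² = 0.531
- active 0.441 + 0.09 × 1.5² = 0.6435
- pooled SD √0.587 = 0.766
- noncentrality 0.45/(0.766 × 0.2) = 2.94, power 74.4%

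| m (mm, assumed) | Power, 10% dropout | Power, 20% dropout |
|---|---|---|
| 0.5 | 81.8% | 71.7% |
| 0.8 | 77.8% | 63.9% |
| 1.0 | 74.4% | 58.1% |
| 1.5 | 64.5% | 44.0% |

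Simulating the mixture (20,000 runs) gave 77.7%, 74.3% and 63.9% for m = 0.8, 1.0 and 1.5 at 10% dropout. That checks the formula, not the assumptions. Giving dropouts an SD of 0.7 mm lowers the 10% column to about 78%, 74%, 71% and 61%.

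**5. If imputed pockets keep part of the improvement.** With a retained fraction f, the difference is 0.5(1 − d) + 0.5df, and μ in the variance becomes (1 − f)μ. At 10% dropout, power returns to 85% at:
- f ≈ 0.31 for m = 0.8 mm
- f ≈ 0.37 for m = 1.0 mm
- f ≈ 0.50 for m = 1.5 mm

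**The case against.** The strongest reply is that little is lost on the documents' own inputs. At the SAP's 10%, dilution alone gives 82% to 84%, or 1.5 to 3 points below 85%. Anything lower needs a placebo-arm reduction that no document states. SAP 2.6 never says that 0.7 mm is the completers' SD; if both 0.5 mm and 0.7 mm already describe the analysed data, nothing is lost. SAP 8.1.1 does not say whether the screening value can be the worst observation; if only values after SRP count, dropouts may keep some response. The primary model is also a tooth-site GEE adjusted for baseline PD, site, smoker status and the smoker-by-treatment interaction. If covariates explained 20% of the variance (an illustration only), the 78%, 74% and 64% at 10% dropout would become about 87%, 84% and 75%. Finally, the SAP requires 95% confidence intervals and a per-protocol repeat, so a null result need not be judged on power alone.

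Much of this stands, and it limits the size of the point. It does not restore the 85%. If dropouts were already in the 0.5 mm and 0.7 mm, the dropout allowance would have no purpose. SAP 8.1.1 sets no post-baseline limit on the worst observation, and a patient with no measurement after SRP has only the screening value to carry. The GEE may help or hurt, but the protocol's 85% to 90% is asserted rather than derived.

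A reader might infer that power at the SAP's 10% dropout simply is 64% to 78%, or about 74%, or 20 points below the stated value. The documents do not support that. Those values need m of 0.8 to 1.5 mm, no retained improvement, and 0.7 mm read as the completers' SD; the 20-point gap is the worst corner. Nor does recovering 85% always require half the improvement to be retained: that holds only at 1.5 mm.

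**Conclusion.** The mismatch is real and lies in the text: the sizing removes dropouts, and the primary analysis keeps them. The 44 and the 10% allowance are arithmetically sound, so this is an unstated planning assumption rather than a calculation error.

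Its size is conditional:
- **Dilution only:** about 82% at 10% dropout and about 72% at 20%, given equal dropout, no treatment effect in dropouts and SD held at 0.7 mm.
- **With the added variance in step 4:** about 82% down to 64% at 10%, and about 72% down to 44% at 20%, for an assumed placebo completer reduction of 0.5 to 1.5 mm.
- **With partial retention:** smaller losses, and possibly none at 10%.

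Rescued pockets are not in these figures. All are subject-level t-test approximations, which the adjusted site-level GEE could shift in either direction. They show that 85% was not derived for the planned test. They do not establish one correct replacement, and they do not by themselves call for more patients.

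**What to change.** In SAP 2.6, the SAP synopsis and Protocol 7.2 (with the matching Protocol synopsis text), do one of the following:
- State that 85% refers to completers and is not the power of the primary ITT test.
- Restate power for the ITT analysis under the SAP 8.1.1 imputation, as a range with its assumptions shown: dropout rate, expected placebo-arm change, what the 0.7 mm SD describes, and whether the screening value counts as the worst observation.

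In either case, use one reconciled dropout rate in place of 10% and 20%, and remove the protocol's 85% to 90% statement. Do not insert a single figure such as 74%, which would write an unsourced placebo response into the plan.

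The cost is a few sentences and a less favourable stated power. Enrolment does not change.

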3. GENERAL ANALYSIS AND REPORTING CONVENTIONS

For continuous endpoints, the summary statistics will generally include number of subjects with data (n), mean, standard deviation, median, minimum and maximum. No preliminary rounding will be performed; rounding will only occur after analysis. To round, the digit to right of last significant digit will be considered: if < 5 then round down, if ≥ 5 then round up. Means and medians will be presented with one more decimal place than the precision of the data. Standard deviations will be presented with two more decimal places than the precision of the data. Percentages will be presented with one decimal place. Minimums and maximums will be presented with the same precision as the original data.

For categorical endpoints, the summary statistics will generally include: number of subjects randomized and/or dosed, number of subjects with data, and the percentage of those with data in each category. Frequency distributions will be presented as appropriate.

Analysis of the clinical efficacy data will consist of modeling endpoints, including change from baseline in PD, CAL, BOP, and FMPI, with treatment group, patients, smoking status, and investigational site as main effects and adjusting for baseline values of a given endpoint. Post-baseline treatment comparisons will be modeled through a GEE method (with a linear link and exchangeable covariance matrix), adjusting for the baseline value. Methods of analysis for periodontal flora, inflammatory cytokine levels in GCF and in serum, and RBL will be described in separate statistical analysis plans.

Hypothesis testing, unless otherwise indicated, will be two-sided. When confidence intervals are presented, they will be two-sided with a confidence coefficient of 95%. Actual P-values will be reported to 3 decimal places if greater than 0.001. If less than 0.001, the value ' <0.001 ' will be reported.

The statistical software, SAS[®] version 9.3 or above, will be used for all summaries and statistical analyses.

4. ANALYSIS POPULATIONS

Statistical analyses will be based on the analysis populations as defined below:

- Safety population: All randomized subjects who use at least one dose of study drug, regardless of whether or not they undergo any study assessments.
- Intention-to-Treat (ITT) population: All randomized subjects.
- Per Protocol (PP) population: All subjects who use at least one dose of study drug and do not have major protocol deviations as defined in § 5.2.

5. STUDY SUBJECTS

5.1 Disposition of Subjects

Subject disposition will be summarized in tables and listings: overall, by treatment, by smoking status at baseline, and by site.

- The number of subjects screened (overall)
- The number of subjects enrolled and randomized
- The number of subjects treated
- The number of subjects who have completed each visit
- The number of subjects who discontinued study treatment; overall and by discontinuation reason:
 - Adverse Event
 - Death
 - Lack of Efficacy
 - Lost to Follow-up
 - Non-Compliance with Study Duration
 - Physician Decision
 - Pregnancy
 - Progressive Disease
 - Protocol Violation
 - Recovery
 - Screen Failure
 - Study Terminated by Sponsor
 - Technical Problems
 - Withdrawal by Subject
 - Other

5.2 Protocol Deviations

Major protocol deviation information will be maintained separately from the electronic CRF, and exports of these data will be delivered separately from the clinical datasets. A major deviation is one that may affect the outcome, analysis, or interpretation of the study. These deviations may include, but are not limited to, the following: Inclusion/exclusion criteria deviations, randomization deviations, and terminations for lack of compliance. Major protocol deviations will be identified by an expert committee prior to unblinding the study. Protocol deviations can be self-reported, recorded following interim monitoring visits, or following remote monitoring. For the per protocol analysis all subjects with minor deviations will be included. All subjects with major deviations will be reviewed as described above and will not be included in the per protocol analysis.

Subjects who miss 20% or more of their prescribed treatments will be considered non-compliant and will be excluded from the per-protocol statistical analysis.

6. DEMOGRAPHIC AND OTHER BASELINE CHARACTERISTICS

Baseline data (demography, medical history, dental history, and baseline disease characteristics) will be summarized.

Demography includes age, sex, race, and ethnicity. Sex, race, and ethnicity will be tabulated in frequencies and continuous summary statistics will be presented for age at screening. Data will also be presented in a listing.

The number and percentage of subjects with each medical history event will be presented by body system and event term. A listing will also be created which will include the body system, event term, whether the medical history event is ongoing and controlled, as well as the start and end dates of the event and any associated comments.

The number and percentage of subjects who have been diagnosed with periodontitis, abscesses, or who have had any oral surgeries or root canals, or are currently experiencing dental pain will be presented. A listing will also be created which will include the above events as well as their associated dates, the date the subject last visited a dentist or hygienist, frequency of flossing and mouth rinse, and interdental irrigation devices.

Results of the baseline oral exam will be listing by area examined and will denote an abnormal or normal result; and, if abnormal, the associated description of the abnormality will be listed. The presence of periodontal abscess or endodontic abscess will also be presented.

Tooth status at baseline will be presented in a listing by subject and tooth, and will denote whether the tooth is missing, sound, decayed, filled, fractured, has a crown, and/or is an implanted tooth.

Quadrants completed during the scaling the root planing procedure at visit 3 will be presented in a listing.

Demographic and baseline disease characteristics will be presented for the safety population.

7. MEASUREMENTS OF TREATMENT COMPLIANCE

Every treatment application of study drug will be performed in the dental clinic by the clinician/investigator (dental professional); therefore, the investigator can assess non-compliance based on subject attendance of scheduled treatments.

Missed treatments may be completed if done within the treatment windows described in the protocol.

Subjects who miss 20% or more of their prescribed treatments will be considered non-compliant and excluded from the per-protocol statistical analysis.

Treatment compliance will be calculated as:

$$\left[\frac{(\# \text{ doses completed within } X \text{ days (with "X" as defined above) from original scheduled dose date)}}{(\# \text{ planned doses})} \right] * 100$$

Treatment compliance will be presented by group at each visit and overall using both continuous summary statistics and the following frequency cut-offs: <50%, 50 - 80%, >80% for the ITT population.

Treatment compliance will also be presented in a listing presenting subject, dosing schedule/treatment group, planned dosing day, whether the subject was dosed within "X" days (with "X" as defined above"), actual dosing day, and treatment compliance.

8. EFFICACY EVALUATION

8.1 Overview of Efficacy Analysis Issues

8.1.1 Handling of Dropouts or Missing Data

All reasonable efforts will be made to minimize missing data. However, there are two possibilities for data being missing. In one case, the measurement associated with an individual pocket may be missing at an evaluation. In this case, the worst previous value for this variable will be imputed for that tooth/pocket. Furthermore, the data from an entire patient may be missing because they withdrew before completing the study. For this imputation, an approach similar to that for each site will be employed. For visits that would follow a patient's premature discontinuation from the study, the worst observation associated with each individual pocket will be imputed for all subsequent visits for that patient and will thus also be carried forward for the 270-day evaluation. Subjects who drop out of the study will not be replaced.

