## 11. ASSESSMENT OF EFFICACY

### 11.1. Criteria for Primary and Secondary Efficacy Endpoint Evaluations:

- a. Pocket Depth (PD): Periodontal pocket depth will be determined with a UNC-15 periodontal probe at 6 sites per tooth, and rounded to the next lower whole millimeter.
- b. Clinical Attachment Level (CAL): The measurement of the position of the soft tissue in relation to the cemento-enamel junction (CEJ) that is a fixed point, using probing depth and the distance from the gingival margin to the CEJ.
- c. Bleeding On Probing (BOP): Dichotomous score of 0 or 1 indicating whether the site bleeds upon probing is performed independently of the gingival index measurement. Bleeding on probing will be measured from the 6 sites of the tooth as a secondary periodontitis variable:

0 = No bleeding

1 = Bleeding within 15 seconds following probing

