At each evaluation, medical and dental history will be updated, an oral exam will be performed, and AEs and SAEs will be assessed and recorded. PD, CAL, and BOP will be evaluated at screening and on Days 15, 30, 60, 90, 180, and 270. Subjects will have urinalysis in addition to blood tests including hematology and chemistry (liver and kidney function) panels done at screening and repeated at Days 90 and 270. FMPI will be recorded at baseline and on Days 15, 30, 60, 90, 180, and 270. Inflammatory cytokines in serum will be measured at baseline and on Days 15, 90, 180, and 270. GCF will be collected and analyzed at baseline and on Days 15, 90, 180, and 270. Microbial analysis of periodontal flora will be performed at baseline and on Days 15, 90, 180, and 270.

At each treatment visit, in addition to administration of ST266 or placebo, medical and dental history will be updated, AEs and SAEs will be assessed and recorded, concomitant medications will be recorded, and oral hygiene instruction will be provided.

Randomization will be stratified by site and smoker status (never smoked or quit smoking more than two years ago vs. has smoked within the last two years). Randomization will be blocked such that assignment to treatment groups both within sites and within smoker status will be approximately even (1:1:1). ST266 will be supplied to the study site and prepared for use by trained clinical staff, who will not be the same as the dental professionals evaluating the subjects.

Primary Endpoint: The primary endpoint of this study is the average change from baseline in tooth site PD for each patient at 9 months (Day 270) in tooth sites with baseline PD \geq 6mm. The change in pocket depth at each tooth site will be the dependent variable with the average over all tooth-sites for each patient being estimated by the statistical model.

Secondary Endpoints: The secondary endpoints of this study are:

- change from baseline in CAL at 270 days in tooth sites with baseline PD \geq 6mm
- change from baseline in BOP for each patient at 270 days. BOP for each patient is calculated as the percent of tooth sites in the whole mouth with bleeding on probing.

Baseline refers to the initial measurement of the endpoint, which may occur at the screening or baseline visit according to the schedule of assessments.

Safety Endpoints: The safety endpoints are the frequency and pattern of AEs and SAEs.

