8.2 Efficacy Variables

Table 8-1 Efficacy Variables and Analysis Methods

Efficacy Variables	Method 1^a
Primary	
Pocket Depth	Δ from baseline at Day 270 in tooth-sites with baseline PD ≥ 6 mm ^a
Secondary	
Clinical Attachment Level	Δ from baseline at Day 270 in tooth-sites with baseline PD ≥ 6 mm ^a
Bleeding on Probing	Δ from baseline at Day 270 using whole mouth average percentage of site with bleeding on probing ^b

^a Generalized Estimating Equations will be used as the primary analytical method. The dependent variable will be change from baseline to Day 270 and the model will include treatment group, patients, smoking status, and investigational site for a given endpoint. A linear link and exchangeable covariance matrix will be employed. Only treatment comparisons at Day 270 will report a p-value. Comparisons at other time points will only present the point estimate and 95% confidence interval. The analyses will incorporate all data from individual tooth sites within each subject.

^b ANCOVA will be used for the analysis of this variable. The dependent variable will be change from baseline to Day 270 and the model will include treatment group, patients, smoking status, and investigational site for this endpoint. Only treatment comparisons at Day 270 will report a p-value. Comparisons at other time points will only present the point estimate and 95% confidence interval.

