8.3.2 Secondary Efficacy Analyses

Additional secondary efficacy analyses will be performed to test the effects of treatment group and their interactions on the secondary endpoints of the change from baseline in CAL and BOP at Day 270. For the CAL analysis, the GEE analyses will be performed with the same statistical model as described in the primary PD efficacy analysis but with the change from baseline in CAL of tooth-sites with baseline PD ≥ 6 mm as the dependent

variable. Separate hypotheses will be performed for testing the treatment effects of group 1 versus group 3 (placebo) and group 2 versus group 3 (placebo). As described above, this model will include the baseline smoker status (smoker or non-smoker) by treatment group interaction. For the secondary efficacy analyses of the BOP change from baseline, ANCOVA will be performed with treatment group as the main effect, and covariates for baseline PD, site, patients, smoker status, and the baseline smoker status (smoker or non-smoker) by treatment group interaction. Point estimates and 95% confidence intervals will be presented for the treatment group differences in CAL and BOP change from baseline at Day 270 and by baseline smoker status.

The CAL and BOP secondary analyses described above will be tested hierarchically in the order of: CAL change from baseline at Day 270, and BOP (presented as a whole mouth average percentage) change from baseline at Day 270. The treatment effects for the CAL or BOP change from baseline at the Day 270 Visit will be compared between Treatment Group 1 and Placebo, and between Treatment Group 2 and Placebo. The alpha will be set at 0.025 to allow for the Bonferroni correction for 2 multiple comparisons for secondary endpoints. Since the smoker status by treatment group interaction is acting as a gatekeeper for further inference testing by smoker status, no additional corrections will be made for multiplicity for any additional analyses of the effects of treatment on CAL and BOP by smoker status. These analyses will be performed once all the subjects (excluding those withdrawn) completed their 270-Day Visit.

All primary and secondary analyses performed on the ITT population will be repeated using the per protocol population.

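### Pocket-by-pocket worst-value imputation turns a dropout's whole-mouth BOP into the share of sites that ever bled, so the penalty depends on how often the subject was examined

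*SAP*

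**What the plan says.** SAP 8.1.1 gives two imputation rules, both at pocket level. For a single missing measurement, "the worst previous value for this variable will be imputed for that tooth/pocket". For a subject who withdraws, "the worst observation associated with each individual pocket will be imputed for all subsequent visits for that patient", and this value "will thus also be carried forward for the 270-day evaluation". No variable is excepted, and no rule is given for a quantity computed per subject.

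Protocol 11.1 defines BOP at a site as a "Dichotomous score of 0 or 1 indicating whether the site bleeds upon probing", with 1 meaning bleeding. SAP 2.2 forms the endpoint as follows: "BOP for each patient is calculated as the percent of tooth sites in the whole mouth with bleeding on probing". SAP Table 8-1 and 8.3.2 agree, the latter naming "BOP (presented as a whole mouth average percentage) change from baseline at Day 270" as the second step of the secondary hierarchy. (The SAP synopsis can be read as limiting BOP to pockets of at least 6 mm. I follow the body of the SAP.)

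On timing, "PD, CAL, and BOP will be evaluated at screening and on Days 15, 30, 60, 90, 180, and 270". A dropout can thus have a screening value and up to five post-SRP values before Day 270. The early-withdrawal visit in Protocol 8.4 can add one more. SAP 8.3 places the test in the ITT population, so dropouts count.

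**The concern.** A worst-value rule is normally a deliberate penalty: the dropout gets the worst state actually seen. Taking the worst of a 0/1 score site by site and then averaging over sites does something else. It collects into one figure every site that bled on any occasion, which may be a state the mouth was never in. The penalty then depends on the number of examinations as well as on disease.

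At stake is a secondary endpoint tested at 0.025 for each active arm against placebo. If arms differ in how many subjects leave, or when, part of that difference would show up as a BOP difference. Even with balanced dropout, a group of subjects with large artificial increases widens the BOP distribution and costs power.

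**Working it through.** **Plan's own figures.** The SAP states no figure for BOP or for the effect of imputation. Its one computed figure, 44 per group for PD, reproduces (42.1 before rounding by the normal approximation; 44 with the t distribution) and does not bear on this point.

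**Step 1: what the rule computes.** Let b(i,v) be 0 or 1 for site i at visit v.

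Imputed BOP = mean over sites of [max over visits of b(i,v)] = share of sites with at least one bleed.

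This follows from the definitions and needs no assumption. Three consequences:

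- It is at or above the whole-mouth percentage at every recorded visit. It equals the worst visit only if a single visit exists or the sites bleeding at the other visits all lie within those of the worst visit.
- Adding a visit can raise it or leave it unchanged, never lower it.
- If screening counts as an observation, which the text does not exclude, a dropout's change from baseline cannot be negative.

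**Step 2: size.** The documents give only the entry criterion of more than 30% bleeding sites, so the rates are assumed: 50% at screening and 30% at each post-SRP visit (true change −20 points). For independent sites and k post-SRP visits:

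- Screening counted: 1 − (1 − 0.5)(1 − 0.3)^k. For k = 5: 1 − 0.5 × 0.168 = 0.916. For k = 1: 1 − 0.5 × 0.7 = 0.65.
- Post-SRP visits only, k = 5: 1 − 0.7^5 = 0.832.

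If the same sites tend to bleed each time, the value is lower. With a probit model and a latent within-site correlation:

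| Latent correlation | 0 | 0.3 | 0.6 | 0.8 | 0.9 |
|---|---|---|---|---|---|
| Screening + 5 visits | 92% | 80% | 68% | 59% | 53% |
| Screening + 1 visit | 65% | 61% | 56% | 53% | 51% |
| 5 post-SRP visits only | 83% | 71% | 59% | 50% | 44% |

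Other assumed rates, independent sites, screening plus five visits: 83.6% (50% then 20%), 59.3% (31% then 10%), 95.0% (70% then 30%).

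**Step 3: how often the excess is strict.** With rates 50% then 20%, 144 sites and five post-SRP visits, the imputed value exceeded every recorded visit in all simulated subjects at correlations 0.3 and 0.6, in 68% at 0.9, and in none at 1.0.

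**Step 4: shift in the arm mean per 10% of dropouts** (rates 50% then 30%).

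- Against a true 30%, screening counted: 0.1 × (92 − 30) = 6.2 down to 0.1 × (53 − 30) = 2.3 points after five visits; 0.1 × (65 − 30) = 3.5 down to 0.1 × (51 − 30) = 2.1 after one.
- A whole-mouth worst-visit rule that counts screening would itself give 50%. The part due to site-wise pooling is therefore 0.1 × (92 − 50) = 4.2 down to 0.1 × (53 − 50) = 0.3 after five visits, and 0.1 × (65 − 50) = 1.5 down to 0.1 × (51 − 50) = 0.1 after one.
- Post-SRP visits only, five visits: 0.1 × (83 − 30) = 5.3 down to 0.1 × (44 − 30) = 1.4. With one post-SRP visit there is nothing to pool.

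**Step 5: spread.** Assume a within-group SD of 15 points and 20% late dropouts whose mean is D points above completers. Arm SD = √(15² + 0.2 × 0.8 × D²). D = 92 − 30 = 62 gives 29. D = 68 − 30 = 38 gives 21. D = 53 − 30 = 23 gives 18.

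**The case against.** **The level of imputation for BOP is inferred.** SAP 8.1.1 never says that bleeding is imputed by site before the percentage is formed, and Table 8-1 defines the analysed variable as "Δ from baseline at Day 270 using whole mouth average percentage of site with bleeding on probing". A programmer could impute the subject's percentage directly. This stands as an ambiguity, but the pocket rule is the only one written, so following the text gives the result above.

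**The rule is meant to be harsh.** This is partly right. If screening counts, much of the shift in Step 4 would arise under any worst-visit rule. What harshness does not explain is dependence on the number of examinations.

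**The consequence is limited.** BOP is the second secondary endpoint in a Phase 2a trial, and a per-protocol repeat is planned. The repeat mitigates only in part, since late leavers may have received more than 80% of their treatments.

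A reader might also infer stronger statements that the documents do not support:

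- *The imputed value always lies above every visit.* It is at or above.
- *Staying longer always scores worse than leaving early.* This holds within a subject as visits are added. It is not a guaranteed ordering between subjects.
- *Every 10% of dropouts costs 4 to 6 points.* That needs all of them to leave after the Day 180 visit and a site correlation no higher than 0.6. No document gives a correlation.
- *The rule favours one arm.* Dropout by arm is not given. Protocol 13.2 links dropout to the number of in-office treatments. Group 2 has about 13 × 2 + 5 = 31 (taking 3 months as 13 weeks) against 5 + 5 + 2 + 7 = 19 in Groups 1 and 3. Imbalance is plausible for Group 2 against placebo, but not established.

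**Conclusion.** The concern holds. The stated rule, applied to a 0/1 site score and then averaged, scores a dropout as the share of sites that ever bled. The mechanism needs no assumption; the size does.

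Under the assumed rates and correlations from 0 to 0.9, with screening counted, 10% dropout moves an arm's mean BOP change by about 2 to 6 points. The site-wise pooling accounts for about 0.1 to 4 of these. The low end applies when nearly the same sites bleed each time or subjects leave early. A 20% versus 10% dropout split between arms (the protocol's and the SAP's planning rates, used here only as an illustration) would produce a spurious BOP difference of that size. With equal number and timing of dropouts and similar bleeding rates, the shifts largely cancel between arms and the cost is variance.

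The change should be made before unblinding. It concerns a secondary endpoint; primary PD and CAL are not percentages of a 0/1 score and do not have this problem.

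**What to change.** In SAP 8.1.1, add a rule for BOP:

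1. For subjects who discontinue, impute the whole-mouth BOP percentage at subject level, as the worst whole-mouth percentage recorded at any single visit, and do not build it from pocket-level worst values.
2. State separately whether screening counts. If it does not, use the screening value for an ITT subject with no post-SRP measurement, who would otherwise have no value.
3. If isolated sites are missing at an attended visit, compute the percentage from the sites observed at that visit, so that one unread site does not displace a recorded visit.

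In SAP 8.1.2.1, state how rescued sites enter the BOP percentage, because that section also assigns site-wise worst scores in the secondary analyses and the two rules should agree.

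In the worked example the imputed value becomes about 50% with screening counted. Without screening it is about 34 to 38% (five visits, 108 to 168 independent sites, visit-to-visit SD 0 to 5 points), and somewhat lower if sites are strongly correlated.

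The cost is a few sentences and a small change to the derivation program. Two drawbacks remain: BOP would be imputed at a different level from pocket-level PD and CAL, and a maximum over visits still rises slightly with attendance.
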